#### **13.1.2 Secondary Endpoint**

- Clinical benefit rate (CBR) estimated by proportion of evaluable patients who had complete response (CR), partial response (PR) or stable disease (SD) as their best response to treatment by PCWG3 criteria in Arm A.
- Duration of response (DOR), duration of therapy (DOT), and time to progression (TTP) among responders by PCWG3 criteria in Arm A.
- Overall survival (OS) in Arms A..
- Safety endpoints include the number and severity of adverse events by CTCAE 5.0 in all

Arms.

### 13.1.3 Exploratory/Translational Endpoint

- Efficacy (6-month PFS, ORR, CBR, ORR, DOR, DOT, TTP, OS) of atezolizumab alone and abemaciclib alone in the CDK12 loss cohort (Arm C).
- From mandatory on-treatment tissue biopsies:
  1. Assessment of FoxP3+/CD8+ ratio in each treatment arm by multiplex immunofluorescence (primary biomarker endpoint).
  2. Assessment of FoxP3+/CD8+ ratio in on-treatment tumor biopsies compared to archival tissue specimens by multiplex immunofluorescence in each treatment arm.
  3. Correlation of AR aberrations (specifically, AR variants and AR amplifications) detected by targeted exome-sequencing or whole transcriptome sequencing with response and resistance to therapy.
  4. Correlation of genomic features (including alterations in CDK4/6 and DNA damage repair pathways, mutational load, neoantigen burden) detected by targeted exome sequencing with response and resistance to therapy.
  5. Assessment of markers of AR pathway activation, pharmacodynamic markers of CDK4/6 inhibition as well as DNMT1 and genes involved with antigen presentation and interferon signaling through whole transcriptome sequencing.
- From plasma collected pre-treatment, on-treatment (6 weeks after starting therapy), and at progression (“Liquid-biopsies”):
  1. Correlation of AR aberrations (specifically, AR variants and AR amplifications) between circulating blood exosomes and tumor tissue.
  2. Correlation of genomic features (including alterations in CDK4/6 and DNA damage repair pathways, mutational load, neoantigen burden) between circulating blood exosomes and tumor tissue.

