## 1.4 Exploratory/Translational Objectives

- To assess the efficacy of atezolizumab alone and abemaciclib monotherapy in the CDK12 loss cohort (Arm C).
- Primary translational objective: To assess FoxP3+/CD8+ ratio in all biopsy specimens and the change between pre-treatment and on-treatment specimens will be reported descriptively for each treatment arm separately (all Arms).
- To perform detailed profiling of tumor immune infiltrate from paired baseline (where available) and on-treatment tumor biopsies in biomarker-unselected and CDK12 mutant cohorts (all Arms).
- Evaluate changes in androgen-receptor signaling pathway with exposure to abemaciclib monotherapy and abemaciclib in combination with atezolizumab (all Arms).
- Identify the biomarkers of response and resistance to abemaciclib monotherapy and in combination with atezolizumab in biomarker-unselected patients (Arms A and B).

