## **2.4 Correlative Studies Background**

### **2.4.1 ImmunoProfile**

Based on pre-clinical studies suggesting that abemaciclib can alter the immune microenvironment in tumors (26, 29), we plan to characterize immune infiltrate in biopsy specimens obtained 6 weeks after starting on trial therapy using the ImmunoProfile assay at Dana-Farber Cancer Institute (DFCI). This assay is already being used to develop an in-depth database of immunoprofiles for all patients seen at DFCI, Brigham and Women's Hospital, and Boston Children's Hospital to better predict response to immunotherapies. This is an optimized multiplex immunofluorescence assay performed in a Clinical Laboratory Improvement Amendments (CLIA) environment with standardized reporting across all samples for research or standard clinical care. The report includes levels of a particular biomarker in both tumor and tumor-stroma interface compartments; PD-L1 expression is reported for both malignant cells and inflammatory cells. As a research test in the same environment, we plan to assay for FoxP3, CD8, PD-L1, and Granzyme B expression, with DAPI as a counterstain. FoxP3 is a marker of regulatory T cells, whereas CD8 is a marker of cytotoxic T-cells; Goel et al. (26) reported a significant decrease in FoxP3+/CD8+ ratio in a tumor model with abemaciclib treatment compared to vehicle control, which was proposed to be one mechanism by which CDK4/6 inhibition may synergize with anti-PD1/PD-L1 checkpoint inhibitor immunotherapy.

The primary biomarker endpoint of this study is the change in FoxP3+/CD8+ ratio in on-treatment biopsy specimens compared to matched archival metastatic biopsy specimens from the same patient (when available) in patients treated with abemaciclib and atezolizumab (arm B) or with abemaciclib alone (arm A). We will also explore correlation of immune infiltrate with genetic features as described below.

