### **9.1.1 Archival (pre-treatment) Specimen Requirements**

Tissue from the most recent metastatic biopsy specimen is preferred, though tissue from primary prostate specimen is allowed if obtained after a patient developed metastatic disease. (Tissue from primary prostate tissue obtained prior to development of metastatic disease is not relevant to these studies.)

The ImmunoProfile assay utilizes 5-micron FFPE slides. Submit 5 unstained slides- if 5 slides are unavailable, submit at minimum either 3 unstained slides or 2 unstained slides with the adjacent H&E slide.  $\geq 50\%$  tumor tissue on each slide is preferred – thus if multiple biopsy specimens were obtained from a patient, the specimen to be sent should be prioritized by 1) metastatic (as opposed to primary) biopsy site 2) tumor content and 3) time interval prior to trial start (more recent specimens preferred).

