## **9.4 Analysis Plan for Correlative Studies**

### **9.4.1 Immune infiltrate from tumor biopsies**

An exploratory endpoint for this study is FoxP3+/CD8+ ratio paired differences between pre-treatment archival tissue and on-treatment biopsies. These paired differences will be compared between the unselected monotherapy group and the combination therapy group. We estimate that 15 patients will have evaluable pre-treatment and on-treatment biopsies per treatment group. In this case, the study will have at least 80% power to detect an effect size of 1.1 using a two-sided Mann-Whitney test at a 0.05 significance level. We are confident that both these effect size estimates are attainable and are clinically meaningful in this study population.

We will also explore correlation of immune infiltrate with genetic features as described below.

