### **13.5 Statistical Plan for Primary Exploratory Endpoint Requiring Biopsies**

The primary biomarker study from the mandatory on-treatment biopsy for unselected mCRPC will be FoxP3+/CD8+ T-cell ratio. We expect the ratio of FoxP3+/CD8+ T-cells in archival pre-treatment tissue to be ~10% (96). We expect this ratio to decrease to ~5% with abemaciclib monotherapy. With 27 patients in arm A, we expect 22 samples in each arm to be evaluable for this endpoint. The FoxP3+/CD8+\_T-cell ratio in all biopsy specimens and the change between pre-treatment and on-treatment specimens will be reported descriptively in each treatment arm separately. The study will have at least 80% power at a 0.05 significance level to detect an effect size of 0.90 in change in FoxP3+/CD8+ T-cells ratio means between the combination group and the monotherapy group, using a two-sided Mann-Whitney test.

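### The primary biomarker endpoint is the on-treatment FoxP3+/CD8+ level in 13.1.3 but the change from matched metastatic tissue in 2.4.1; the stated hypothesis is a change, and the baseline tissue rule also differs.

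*Combined protocol and SAP*

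**What the plan says.** Five places in the current text describe this endpoint, and they do not agree.

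- **13.1.3**, under "From mandatory on-treatment tissue biopsies", lists as item 1 "Assessment of FoxP3+/CD8+ ratio in each treatment arm by multiplex immunofluorescence (primary biomarker endpoint"). Item 2, without the primary label, is "Assessment of FoxP3+/CD8+ ratio in on-treatment tumor biopsies compared to archival tissue specimens by multiplex immunofluorescence in each treatment arm".
- **2.4.1**: "The primary biomarker endpoint of this study is the change in FoxP3+/CD8+ ratio in on-treatment biopsy specimens compared to matched archival metastatic biopsy specimens". The sentence goes on to require the same patient, where tissue is available, and covers Arms A and B.
- **1.4** sets the primary translational objective as "To assess FoxP3+/CD8+ ratio in all biopsy specimens and the change between pre-treatment and on-treatment specimens", so it holds both measures.
- **9.4.1** gives the paired measure a lower rank: "An exploratory endpoint for this study is FoxP3+/CD8+ ratio paired differences between pre-treatment archival tissue and on-treatment biopsies". It plans to compare these differences between the monotherapy and combination groups, with 15 evaluable pairs per group.
- **13.5** takes about 10% as the expected ratio in archival tissue and states "We expect this ratio to decrease to ~5% with abemaciclib monotherapy". It expects 22 evaluable samples per arm and reports ratio and change descriptively by arm. It then gives 80% power for a combination-versus-monotherapy test.

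On the baseline specimen, 9.1.1 prefers metastatic tissue, but "tissue from primary prostate specimen is allowed if obtained after a patient developed metastatic disease". Arm B closed at 8 patients, and Arm A now enrols without randomization (Synopsis, 1.1).

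**The concern.** A reader following 13.1.3 would report the on-treatment ratio as the primary biomarker result. A reader following 2.4.1 would report the within-patient change. These are different quantities. The hypothesis concerns the second, because a fall from about 10% to about 5% needs a pre-treatment value. An on-treatment ratio from a single arm has no internal contrast. Its only reference is the 10% figure that 13.5 takes from a cited source.

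The baseline has a similar gap. If the archival sample is primary prostate and the on-treatment sample is a metastasis, a difference between tissue sites could be confounded with a drug effect. No section says how such pairs are to be analysed. At stake is the interpretation of the one measure that speaks to the proposed immune mechanism.

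**Working it through.** **The plan's own power figures.** Both use a two-sided Mann-Whitney test at 0.05. I used the noncentral t distribution, with n scaled by the Mann-Whitney relative efficiency 3/π = 0.955, and checked it with 20,000 simulated trials with normal data.

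- 13.5, 22 v 22, effect size 0.90: 0.812 (simulation 0.818).
- 9.4.1, 15 v 15, effect size 1.1: 0.810 (simulation 0.796).

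Both agree with the stated 80%, but only for two full arms. At the 22/27 evaluable rate in 13.5, Arm B would supply 8 × 22/27 = 6.5 patients. Simulated power at 0.90 is then 0.50 for 22 v 8, 0.49 for 22 v 7 and 0.42 for 22 v 6. The effect detectable with 80% power rises from 0.90 to between 1.23 (8 patients) and 1.37 (6 patients) SD. The two evaluability figures also matter: with 15 pairs per group rather than 22, power at 0.90 would be 0.64 even with two full arms.

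**What each measure can estimate.** The hypothesised effect is the ratio of on-treatment to pre-treatment value, about 5/10 = 0.5. The paired change estimates this directly. The on-treatment level estimates only its numerator, and a larger n does not supply the denominator.

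**Precision of the paired change.** Inputs: n = 15 pairs (9.4.1); true ratio 0.5, so |log ratio| = ln 2 = 0.693; SD of the log change is not in the documents and is assumed at 0.5, 0.8 and 1.2.

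- Half-width of the 95% CI on the log scale = t(0.975, 14) × SD/√15 = 2.145 × SD/3.873. The CI factor is its exponential.
- Power: two-sided paired t test at 0.05, noncentrality = (0.693/SD) × √15.

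| Assumed SD | Half-width | 95% CI factor | Noncentrality | Power for a true halving |
|---|---|---|---|---|
| 0.5 | 0.277 | ×/÷ 1.32 | 5.37 | 0.999 |
| 0.8 | 0.443 | ×/÷ 1.56 | 3.36 | 0.88 |
| 1.2 | 0.665 | ×/÷ 1.94 | 2.24 | 0.55 |

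**Fewer pairs.** The 15 pairs in 9.4.1 are not limited to metastatic tissue. With 10 pairs, a number chosen only for illustration, the same power calculation gives 0.97, 0.68 and 0.37.

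**The case against.** The strongest reply is that little turns on the label. The change will be produced under 1.4, 13.1.3 item 2 and 13.5 whichever item is called primary. The per-arm plan is descriptive, the endpoint is exploratory, and no decision rule uses it. All of that stands, and it makes this a minor point.

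The reply also holds against four stronger readings that a reader might infer:

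- *That the plan cannot measure the drug effect.* This is true of item 1 alone, not of the plan.
- *That the level was a sound primary measure while Arms A and B were being compared.* The documents do not support this. The surviving comparison text in 9.4.1 and 13.5 compares changes, not levels. Both arms also received abemaciclib, so a contrast between them would have shown what atezolizumab added, not what abemaciclib did.
- *That mixed tissue sites bias the result.* Confounding is possible in those pairs, but the documents give no size, direction or frequency. Section 9.1.1 ranks metastatic tissue first and rules out primary tissue taken before metastatic disease. A collection rule in 9.1.1 can coexist with a narrower analysis set in 2.4.1; what is missing is the rule for the other pairs.
- *That 15 pairs would reliably detect a halving.* An estimate exactly at one half would exclude no change in all three SD cases, but a true halving would not always give that estimate. At SD 1.2 the power is about 0.55.

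What the reply does not remove is that two sections name different primary endpoints, and that the one in the statistical section is not the quantity hypothesised.

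**Conclusion.** The point holds as an inconsistency to correct, of minor severity. Sections 13.1.3 and 2.4.1 define the primary biomarker endpoint differently, 1.4 covers both measures, and only the change matches the hypothesis in 13.5. The change is already planned and reported; its rank and its baseline are what remain unsettled.

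The comparison and power text left in 9.4.1 and 13.5 is part of the same problem, because it supposes two full arms. The precision figures rest on assumed SDs, roughly normal log changes and 15 evaluable pairs. They show that the paired endpoint is workable at the two smaller SDs and only moderately informative at the largest.

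**What to change.** 1. In 13.1.3, 13.5 and 9.4.1, name the paired on-treatment versus archival change in Arm A as the primary biomarker endpoint. Report Arm C separately. Align 1.4 and 2.4.1 with this; 2.4.1 still includes Arm B.
2. Report the change with a 95% CI, for example as a geometric mean ratio, in metastatic-to-metastatic pairs. Show all pairs, including those with primary-prostate tissue, as a sensitivity analysis.
3. Keep the on-treatment level as a secondary measure.
4. Delete the monotherapy-versus-combination comparison in 9.4.1 and the Mann-Whitney power sentences in 9.4.1 and 13.5.

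The cost is wording only, with no new visit, sample or patient. The downside is fewer contributors: at most about 15 pairs instead of 22 on-treatment samples, and possibly fewer once the main analysis is limited to metastatic pairs.

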## 13.2 Primary Efficacy Endpoint Statistical Plan and Sample Size

A two-stage design with dichotomous co-primary endpoints 6-month progression-free survival (6m-PFS) and objective response rate (ORR; PSA reduction by greater than 50% or radiographic response by RECIST 1.1) will be used to accrue approximately 27 patients in arm A (95). This study achieves 86% power for 6-month progression-free survival (with null 6m-PFS 12% (7) and alternative of 34%) and 85% power for response (with null ORR 10% (38) and alternative of 30%) simultaneously at a one-sided alpha 0.08. The study will accrue 12 patients at the first stage of arm A and will be terminated with 37% of probability of early stopping if no patient responds and no patient is progression-free at 6 months. The number of patients with 6m-PFS and objective response are independent to each other. Stage 2 will accrue 15 additional patients, leaving a cumulative accrual of 27 patients in arm A. If 6 patients experience 6m-PFS or 5 patients have an objective response by the end of stage 2, this study would suggest meaningful clinical activity.

We assume an accrual rate of 4 patients per month (2 per arm) for all sites combined. Accrual

duration of stage 1 will be 6 months and the enrollment will be paused maximum 6 months after enrolling 12th patient to observe the patient's response. If arm A opens stage 2 then another 8 months will be expected for accrual.

For arm C (CDK12 loss CRPC), similar assumptions will be made with expected efficacy with a null 6m-PFS rate of 12% and an alternative rate of 34% or greater. Due to accrual limitations in this arm, we will use a single stage design. Five patients with CDK12 loss will be accrued to an atezolizumab monotherapy as an exploratory group. Then, additional subjects with CDK12 loss will be accrued to therapy with abemaciclib.

A one-sided, one-sample log-rank test calculated from a sample of 16 subjects treated with abemaciclib alone achieves 80-85% power at a 0.05 significance level to detect a 6m-PFS proportion of 34% in this population with the combined treatments when the 6m-PFS in the historic control group is 12%. Accrual duration will be 18 months, the same period of accrual as arm A. Follow-up continues for 12 months after the last subject is accrued. The expected number of events during the study is 14-16. It is assumed that the PFS time distributions of both groups are approximated reasonably well by the exponential distribution.

For the patients treated with abemaciclib alone in each arm A and C, the 6m-PFS and 90% confidence interval will be estimated using Kaplan-Meier method and ORR with 90% binomial confidence interval will be summarized. The efficacy endpoints of 6m-PFS and ORR in patients treated with combination of abemaciclib and atezolizumab in arm B will be listed individually due to small number.

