Statistical Methodology	
Efficacy Analysis
 
27 total evaluable patients in Arm A will provide 86% power for 6 month progression-free survival (with null 6m-PFS 12% and alternative of 34%) and 85% power for objective response rate (with null ORR 10% and alternative of 30%) and with a one-sided type 1 error of 8%. When 12 patients in Arm A have been enrolled and followed for maximum 6 months, Arm A will close if there is no patient with response or with 6m-PFS. Otherwise, the 2nd stage will open, and 15 more patients will be enrolled in that arm for 8 months for a total of 27 patients. The 6m-PFS Kaplan-Meier estimate for Arm A will be reported with a 90% confidence interval. If 6 patients experience 6m-PFS or 5 patients have an objective response by the end of stage 2, this study would suggest meaningful clinical activity.
 
For Arm C (CDK12 loss CRPC), similar assumptions will be made with expected efficacy with a null 6m-PFS rate of 12% and an alternative response of 34% or greater with abemaciclib therapy. Due to accrual limitations in this arm, we will use a single stage design. Five patients with CDK12 loss will be accrued to an atezolizumab monotherapy as exploratory group. Then, 16 additional subjects with CDK12 loss will be accrued to therapy with abemaciclib for 18 months, the same accrual time as arm A. A one-sided, one-sample log-rank test calculated from a sample of 16 subjects achieves 80-85% power at a 0.05 significance level to detect 22% of difference in 6m-PFS. Follow-up continues for 12 months after the last subject is added. The 6m-PFS Kaplan-Meier estimate will be reported with a 90% confidence interval.
 
Safety analysis
 
Safety and tolerability for abemaciclib monotherapy and for the combination of abemaciclib and atezolizumab will be summarized by rate of dose-limiting toxicities (DLTs) as defined in section 8.3.8 using percentage and 90% confidence interval, and by incidence and grade of adverse events (AEs) by CTCAE version 5.0.
 
Bayesian toxicity monitoring was planned to be used for all patients enrolled to Arm B and to the combination treatment cohort of Arm C (up to a maximum of 43 patients). If the rate of patients experiencing dose limiting toxicities (DLTs) at the starting dose exceeded the pre-specified threshold for excessive toxicity, then subsequent patients randomized to

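### The Arm A stage-1 futility rule stops a drug at both null rates about 6% of the time, not the stated 37%, and no correlation between the endpoints can bring it to 37%

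*Combined protocol and SAP*

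**What the plan says.** Section 13.2 describes a two-stage design for Arm A with co-primary endpoints 6-month PFS and objective response. On stage 1 it says "The study will accrue 12 patients at the first stage of arm A", and that the arm "will be terminated with 37% of probability of early stopping if no patient responds and no patient is progression-free at 6 months". The null and alternative rates are 12% and 34% for 6-month PFS, and 10% and 30% for response. The dependence assumption is explicit: "The number of patients with 6m-PFS and objective response are independent to each other". Stage 2 adds 15 patients for a total of 27. Activity is claimed with 6 patients progression-free at 6 months or 5 responders. The stated operating characteristics are one-sided alpha 0.08 and power of 86% (6-month PFS) and 85% (response).

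The Synopsis gives the same zero rule without the 37%: "Arm A will close if there is no patient with response or with 6m-PFS". Section 1.1 says only that enrolment halts after 12 Arm A patients and resumes if the efficacy threshold is met. Section 13.2 allows the pause to last up to 6 months.

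**The concern.** The 37% is the only figure the plan gives for how well the interim look protects patients from an inactive drug. It is attached to a rule that requires zero successes on both endpoints. With 12 patients and null rates of 10% and 12%, some success by chance is likely, so double zero should be uncommon.

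If 37% is wrong for the written rule, those who approved and oversee the trial have been told of a safeguard that is much weaker in fact. A team applying the text literally would also continue with, say, 1 of 12 responding and 1 of 12 progression-free, a result at which the rule that actually yields 37% would stop. With Arm B closed, Arm A is the only unselected arm still enrolling, and this is its only stated efficacy interim.

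**Working it through.** **Inputs** (all from section 13.2): stage-1 n = 12; null 6-month PFS 0.12; null response 0.10; independence; stop only if both counts are zero; 15 more patients if the arm continues.

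**1. Attempt to reproduce 37% with the written rule.**
- P(0 of 12 progression-free) = 0.88^12 = 0.2157
- P(0 of 12 respond) = 0.90^12 = 0.2824
- Joint, independent: 0.2157 × 0.2824 = 0.0609, or **6.1%**

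**2. Does correlation rescue it?** Let p11 be the probability that a patient has both outcomes. The chance that a patient has neither is 1 − 0.12 − 0.10 + p11 = 0.78 + p11, with p11 between 0 and 0.10.
- Minimum: 0.78^12 = 5.1%
- Maximum: 0.88^12 = **21.6%**

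The maximum equals the smaller marginal, so 37% is out of reach.

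**3. Do other readings rescue it?**
- Stop if either endpoint is zero (a possible literal reading of the Synopsis): 0.2824 + 0.2157 − 0.0609 = 43.7%
- Response alone: 28.2%
- 6-month PFS alone: 21.6%
- Written rule under the alternatives: 0.2% with only PFS active, 0.3% with only response active, about 0.01% with both active

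None gives 37%.

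**4. Which rule does give 37%?** Stop if at most 1 responder and at most 1 progression-free:
- P(Bin(12, 0.12) ≤ 1) = 0.2157 + 12 × 0.12 × 0.88^11 = 0.5686
- P(Bin(12, 0.10) ≤ 1) = 0.2824 + 12 × 0.10 × 0.90^11 = 0.6590
- Product: 0.3747, or **37.5%**

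**5. Consequence under the null.** E[N] = 27 − 15 × P(stop).
- Zero rule, independent: 27 − 15 × 0.0609 = 26.1; continues 93.9% of the time
- Zero rule, maximum dependence: 27 − 15 × 0.2157 = 23.8; continues 78.4%
- At-most-1 rule, independent: 27 − 15 × 0.3747 = 21.4; continues 62.5% (63% on the plan's rounded 37%)

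**6. Full two-stage properties** (exact convolution of 12 + 15 patients, independence):

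| Stop at stage 1 if | Success at 27 if | Early stop, null | Overall alpha | Power, only PFS active | Power, only response active |
|---|---|---|---|---|---|
| 0 and 0 (written) | ≥6 or ≥5 (written) | 6.1% | 21.0% | 94.4% | 94.5% |
| ≤1 and ≤1 | ≥6 or ≥5 (written) | 37.5% | 19.0% | 92.6% | 91.4% |
| 0 and 0 (written) | ≥7 or ≥6 | 6.1% | 8.1% | 86.9% | 86.8% |
| ≤1 and ≤1 | ≥7 or ≥6 | 37.5% | 7.7% | 85.7% | 84.7% |
| *Stated in the plan* | | *37%* | *8%* | *86%* | *85%* |

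The fourth row matches all four stated figures after rounding. Its cut-offs are each one higher than those written.

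**The case against.** Five points can be made for the plan.

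- **The zero rule may be intended.** It appears in both section 13.2 and the Synopsis, and no at-most-1 rule is mentioned anywhere. The design reference is not available here, so the slip may lie in the percentage rather than the rule. This stands: the off-by-one explanation is inferred from the arithmetic. The mismatch between rule and figure is not an inference.
- **The 6% rests on independence.** Both endpoints come from the same patients, and positive dependence would raise the stopping probability. This stands as a qualification, but independence is the plan's own assumption and the ceiling is 21.6%. The at-most-1 rule likewise gives 37% only under independence; it ranges from 35.4% to 56.9% across dependence.
- **The pause may be short.** Six months is a maximum, and a single success on either endpoint settles the zero rule, so enrolment could reopen early. This is fair, and the cost of the pause should not be pressed.
- **Correcting stage 1 does not repair alpha.** With the written success rule, alpha is 19.0% after the change and 21.0% before it. This is right. That error lies in the final cut-offs and is separate, but the two belong together in one correction.
- **The written rule can be carried out, and it is not what drives false-positive claims.** Also right. The harm is an overstated futility safeguard, about 5 extra patients expected under the null (26.1 − 21.4 = 4.7).

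**Conclusion.** The concern holds and must be fixed. At the plan's null rates and under its independence assumption, the written rule stops Arm A with probability 6.1%. Under any dependence the range is 5.1% to 21.6%, so the stated 37% cannot belong to this rule. Inactive here means both endpoints at their stated nulls. The 37% is correct, under independence, for stopping at no more than 1 success on each endpoint. The most likely explanation is that the cut-offs were written one too low, since raising the stage-1 and final cut-offs by one recovers every stated operating characteristic, but the documents do not confirm this. Whichever rule was intended, either the rule or the probability in section 13.2 is wrong.

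**What to change.** In section 13.2 and the Synopsis, choose one of the following.

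- **If 37% is the intended property:** state that Arm A closes after stage 1 if at most 1 of 12 patients responds and at most 1 of 12 is progression-free at 6 months, with null early-stopping probability of about 37% under independence.
- **If the zero rule is intended:** keep it, word it identically in both places as requiring zero on both endpoints, and state the early-stopping probability as about 6% under independence and at most 21.6% under any dependence.

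In either case, reconcile the final success cut-offs in the same amendment and state alpha and power for the full pair of rules.

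The cost is wording plus a small loss of power if the first option is taken. With success at ≥7 or ≥6, power falls by 1.2 points for PFS (86.9% to 85.7%) and 2.1 points for response (86.8% to 84.7%), which lands on the quoted 86% and 85%. With the written ≥6 or ≥5, it falls by 1.9 and 3.1 points and stays above the quoted values, but alpha remains at 19.0%.

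The documents do not show whether the interim look has taken place. If it has, report the rule that was actually applied with its true operating characteristics.

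### The Arm A success rule (6 patients with 6m-PFS or 5 responders out of 27) carries a type I error of about 21%, not the stated 8%; the stated alpha and power belong to thresholds one patient higher

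*Combined protocol and SAP*

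**What the plan says.** Section 13.2 sets out a two-stage design for Arm A with two dichotomous co-primary endpoints, 6-month PFS and ORR. The operating characteristics claimed are "86% power for 6-month progression-free survival (with null 6m-PFS 12% (7) and alternative of 34" per cent) and "85% power for response (with null ORR 10% (38) and alternative of 30" per cent), held "simultaneously at a one-sided alpha 0.08". The Synopsis repeats the two power figures "with a one-sided type 1 error of 8" per cent.

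On stage 1: "The study will accrue 12 patients at the first stage of arm A", and the arm is to be "terminated with 37% of probability of early stopping if no patient responds and no patient is progression-free at 6 months". Fifteen more patients then bring the total to 27. Section 13.2 states that the two counts are taken as independent.

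The final rule has the same wording in both places: "If 6 patients experience 6m-PFS or 5 patients have an objective response by the end of stage 2", the study is taken to indicate meaningful activity. Neither place says that the count must exceed 6 or exceed 5.

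**The concern.** The success rule and the error rates are stated side by side, so one can be checked against the other. With 27 patients and null rates of 12% and 10%, about 3.2 patients with 6m-PFS (27 × 0.12) and 2.7 responders (27 × 0.10) are expected by chance. A bar of 6 or 5, with two chances to clear it, looked too low for an overall alpha of 8%.

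This is the only success criterion for Arm A, and efficacy in Arm A is the first primary objective. A final result of exactly 6 with 6m-PFS (and fewer than 6 responders), or exactly 5 responders (and fewer than 7 with 6m-PFS), would count as positive under the text but not under the design that has the stated alpha.

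**Working it through.** **Inputs (Section 13.2; Synopsis, Statistical Methodology).** n1 = 12, n2 = 15, n = 27. 6m-PFS: p0 = 0.12, p1 = 0.34. ORR: p0 = 0.10, p1 = 0.30. Endpoints independent. No dropout allowance, since 27 are treated as evaluable. Stated results: alpha 8%, power 86% and 85%, early stopping 37%.

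**Method.** Let X and Y be the numbers with 6m-PFS and with a response; X1 and Y1 are their stage-1 values. The arm stops if X1 ≤ a and Y1 ≤ b. Otherwise success is X ≥ r or Y ≥ s at 27 patients. Summing over all stage-1 outcomes that do not stop:

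P(success) = Σ P(X1 = x) P(Y1 = y) × [1 − P(X2 < r − x) P(Y2 < s − y)]

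with X1, Y1 binomial on 12 and X2, Y2 binomial on 15. Alpha sets both endpoints at their nulls. Power for one endpoint sets it at its alternative and the other at its null.

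**Reproducing the plan's figures.** Stage-1 bounds from 0 to 4 for each endpoint were searched together with final thresholds of 5 to 8 (6m-PFS) and 4 to 8 (ORR). Only one combination rounds to the stated alpha and both stated powers, and it also gives the stated early stopping: stop at ≤1 and ≤1, success at ≥7 or ≥6.

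| Rule | Early stopping under the null | Alpha | Power, 6m-PFS | Power, ORR |
|---|---|---|---|---|
| Stated in the plan | 37% | 8% | 86% | 85% |
| As written: stop at 0 and 0; success ≥6 or ≥5 | 6.1% | 21.0% | 94.4% | 94.5% |
| Stop ≤1 and ≤1; success ≥7 or ≥6 | 37.5% | 7.7% | 85.7% | 84.7% |
| Stop at 0 and 0; success ≥7 or ≥6 | 6.1% | 8.1% | 86.9% | 86.8% |
| Stop ≤1 and ≤1; success ≥6 or ≥5 | 37.5% | 19.0% | 92.6% | 91.4% |

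(37.5% is 0.3747 before rounding, which gives 37% as a whole number.)

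**Hand check of the 21%.** Ignoring the interim, P(X ≥ 6 | 27, 0.12) = 0.0966 and P(Y ≥ 5 | 27, 0.10) = 0.1266. Under independence the chance of clearing at least one bar is 1 − (1 − 0.0966)(1 − 0.1266) = 1 − 0.9034 × 0.8734 = 0.211. The interim as written stops with probability 0.88^12 × 0.90^12 = 0.2157 × 0.2824 = 0.061, and hardly any of those trials would have succeeded, so alpha falls only to 0.2098.

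**Each endpoint alone.** With the written interim the two criteria alone give 0.096 (6m-PFS) and 0.126 (ORR). Each exceeds 0.08 by itself.

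**Sensitivity to dependence, written rule.** If every responder is also progression-free at 6 months, alpha is 0.142. If no patient has both outcomes, it is 0.215.

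**Other readings.** If success required both criteria, alpha would be 1.2%, which does not match either.

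**The case against.** Several defences were tried.

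- *The 8% applies to each endpoint.* Each criterion alone already exceeds 8%, and Section 13.2 describes the error rate as simultaneous.
- *Response and 6m-PFS are positively related, so independence overstates alpha.* This is true as far as it goes. The 21% depends on independence, and full nesting lowers it to 14.2%. But independence is the plan's own assumption, and 14.2% is still well above 8%. Under nesting, the 7-or-6 rule with the written interim would be conservative, at about 5.6%.
- *The text could be read as more than 6 and more than 5.* Neither section says so, and on the plain reading 6 or 5 is enough.
- *A success criterion in a phase II trial is only suggestive, and the planned Kaplan-Meier and binomial estimates with 90% intervals do not depend on it.* The estimates are indeed unaffected. The criterion is still the only one given for Arm A, and it contradicts its own stated error rate.

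Two points stand as refinements. First, that cut-offs to be exceeded were copied as counts to be reached is an inference from the numerical match; the documents do not say which the sponsor intended, the counts or the error rates. Second, changing only the final counts leaves the stated 37% early stopping beside a stage-1 rule that stops 6.1% of the time.

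**Conclusion.** The concern holds. Under the plan's null rates, sample sizes, interim rule and independence assumption, the written success rule has a type I error of 0.2098. That is 2.6 times the stated 8% (0.2098 / 0.08), or 2.7 times the 7.7% of the design that matches the stated figures (0.2098 / 0.0771). Power as written is about 94% for each endpoint, so none of the stated alpha, power and early-stopping figures describes the rule in the text. Across the full range of dependence between the endpoints, alpha for the written rule lies between 14% and 22%. Because the mismatch sits in the primary decision rule, it must be corrected.

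**What to change.** In Section 13.2 and the Synopsis, state success as at least 7 patients (more than 6) with 6m-PFS or at least 6 patients (more than 5) with an objective response. Under the plan's assumptions this gives alpha of 7.7% to 8.1% and power of about 85% to 87%, depending on the stage-1 rule.

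In the same edit, reconcile stage 1 with the stated early stopping. Either the bound becomes at most 1 responder and at most 1 patient with 6m-PFS among 12, which fits 37%, or the present bound of none stays and the probability is restated as about 6%, with power of about 87% for each endpoint.

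If 6 and 5 are what the sponsor wants, keep them and restate alpha as about 21% and power as about 94%, with early stopping of about 6%. With the ≤1 and ≤1 stage-1 rule the figures are about 19% and 91% to 93%, with early stopping of 37%.

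The cost is a text amendment in two places, with the IRB approval that Appendix B-3.1 expects for protocol revisions. No patients are added; under the first option the success bar rises by one patient per endpoint. Arm A is still enrolling, so the choice should be made and dated without reference to its accumulating outcomes.
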